5.1.3 Discontinuation of Subjects from the Study

Subjects will be informed that they are free to withdraw from the study at any time. Subjects should be questioned for the reason of premature withdrawal, although they are not obliged to disclose it. This needs to be fully documented in source documents and reported in the CRF.

When a subject is discontinued (withdraws or is discontinued) from the study, the early termination procedure planned ([Section 9](#)) must be performed as soon as possible after the time of discontinuation unless subject withdrew the informed consent to do so. After the time of discontinuation, the subject will enter into a 7-day passive safety FU. Subjects withdrawn or discontinued from the study cannot re-enter the study.

Subjects must be discontinued from the study for any of the following reasons:

- Withdrawal of informed consent.
- Any AE or condition (including clinically relevant changes in a laboratory parameter) at the discretion of the Investigator.
- Positive pregnancy testing (no invasive procedures including the drawing of blood must be performed after detection of pregnancy, see [Section 8.5](#)).
- Female subjects starting contraception or hormone replacement therapy containing estrogens during the study.
- The use of any nicotine/tobacco product which is different from the assigned IP.
- The Sponsor or Investigator terminates the study.
- Discontinuation is considered to be in the best interest of the subject or the other subjects.

Subjects may be discontinued from the study for any of the following reasons:

- Lost to follow-up.
- Non-authorized concomitant medication as defined in the context of this study (in general, any concomitant medication should be discussed with the Contract Research Organization [CRO] Medical Monitor on an ongoing basis).
- Non-compliance to the study procedures.

Subjects discontinued after randomization will not be replaced and will not be allowed to re-enter. All withdrawals and discontinuations have to be documented properly in the CRF.

5.1.4 Violation of Selection Criteria

Subjects who are eligible at the Screening Visit but who do not meet the entry criteria at Admission (Day -2) prior to enrollment will be considered a screening failure.

Data and information contained in this document are considered to constitute trade secrets and confidential commercial information, and the legal protections provided to such trade secrets and confidential information are hereby claimed under the applicable provisions of US law. No part of this document may be publicly disclosed without the written consent of PMI.

6 INVESTIGATIONAL PRODUCTS

6.1 P4M3

6.1.1 Description

The P4M3 will be provided by the Sponsor and its distribution will be controlled by a qualified and appropriately trained designee. P4M3 with e-liquid contains the following concentrations of nicotine with and without lactic acid: 1.7 % nicotine without lactic acid, 1.7 % nicotine with lactic acid, 3 % nicotine with lactic acid, and 4 % nicotine with lactic acid.

P4M3 comprises the following components:

- A Battery (and electronics) Unit, onto which the Cartomizer is mounted.
- A disposable Cartomizer, which contains porous materials, a heater, and the nicotine solution (e-liquid).
- A USB cable to charge the Battery unit from a low voltage port.

6.1.2 Packaging and Labelling

The P4M3 variants will be packaged and labelled appropriately for in-clinic subject use during the study.

6.2 Subjects' Own e-Cigarettes

6.2.1 Description

Subjects will bring their own e-cigarette with e-liquid. Subjects' own e-cigarettes have to be commercially available, closed tank/cartridge e-cigarette. Subject will be asked to buy the anticipated amount of e-cigarette (e-liquid) for the study.

6.3 Use of Investigational Products

Subjects will never be forced to use the products and will be free to stop using the products at any time during the study. Subjects caught using any nicotine/tobacco product which is different from the assigned IP will be discontinued from the study. During the screening period, subjects will be allowed to use e-cigarettes according to their usual habits except during the procedures of the Screening Visit.

6.3.1 Admission (Day -2)

Subjects will be admitted to the investigational site at Admission (Day -2) for assessments and a debriefing on P4M3. Subjects should have been fasting for at least 12 hours prior to Admission. After confirmation of subjects' eligibility, subjects will be enrolled in the study, have a debriefing on

P4M3, and perform a product test with P4M3-1.7% for a maximum of 10 minutes. The product test will be physically connected to the puffing topography device without recording of parameters (HPT device switched off). After the product test, subjects not willing and/or ready to use P4M3 will be discontinued and may be replaced. Following the product test, subjects will be required to abstain from any nicotine/tobacco containing product use for at least 10 hours until the first product use on Day -1.

6.3.2 Baseline (Day -1)

On Day-1, subjects will be instructed to use their own closed tank/cartridge e-cigarette using a fixed puffing regimen in the morning and subsequently, to use it *ad libitum* for 60 minutes in the afternoon. The start time of the product use for each fixed puffing regimen and *ad libitum* use will be defined as start of the first puff (T0). T0 will be at approximately the same time in the morning (± 30 minutes) for fixed puffing regimen and at approximately the same time in the afternoon (± 30 minutes) for *ad libitum* use on Days 1 to 4.

6.3.3 Investigational Period (Day 1 to Day 5)

On Day 1, subjects will be randomized to one of two product use sequences of the P4M3 variants in order to cross-over the use of P4M3-1.7% and P4M3-1.7%LA:

Sequence 1:

P4M3-1.7%; P4M3-1.7%LA; P4M3-3%LA; and P4M3-4%LA

Sequence 2:

P4M3-1.7%LA; P4M3-1.7%; P4M3-3%LA; and P4M3-4%LA

On Days 1 to 4, subjects will be provided and instructed to use a new, ready-to-use product (full cartridge) of the assigned P4M3 variant for fixed puffing regimen with HPT recording in the morning and another new one for the *ad libitum* use for 60 minutes with HPT recording in the afternoon, according to one of two randomly assigned sequences. The concentration of P4M3 e-liquid will be the same on a given day for fixed puffing and *ad libitum* use on Days 1 to 4. T0 for 60 minutes *ad libitum* use should be at least 10 hours after T0 for fixed puffing to allow adequate characterization of nicotine plasma AUCs. There will be a washout of at least 10 hours following each *ad libitum* product use with respect to the subsequent fixed puffing regimen in the next morning to allow adequate background correction of the fixed puffing regimen-related nicotine plasma concentrations.

Following product use on each day, the used e-liquid cartridges will be collected for assessment of e-liquid use. E-liquid cartridges will be weighed prior and post product use.

Except for the test products, subjects will not be allowed to use any nicotine-containing products through Discharge or early termination.

Subjects will be continuously supervised during P4M3 usage.

Data and information contained in this document are considered to constitute trade secrets and confidential commercial information, and the legal protections provided to such trade secrets and confidential information are hereby claimed under the applicable provisions of US law. No part of this document may be publicly disclosed without the written consent of PMI.

6.3.4 Safety Period

During the passive safety FU period, subjects are free to use e-cigarettes according to their usual habits.

6.3.5 Stopping Rules for Investigational Product

For safety purposes, use of the IPs should be temporarily reduced or stopped in the event of any signs suggesting nicotine overexposure, e.g., gastrointestinal disturbance (nausea, vomiting, diarrhea, stomach, or abdominal pain), cold sweats, headache, dizziness, and breathing problems or any reasons at the discretion of the Investigator.

For subjects who are discontinued, the reason for discontinuation should be documented in the source documents and in the CRF and subjects will undertake early termination procedures ([Section 9.5](#)).

6.4 Method for Assigning Subjects to Study Arms

Subjects will be randomized to either one of two sequences of IP exposures:

Sequence 1:

P4M3-1.7%; P4M3-1.7%LA; P4M3-3 %LA; and P4M3-4%LA

Sequence 2:

P4M3-1.7%LA; P4M3-1.7%; P4M3-3%LA; and P4M3-4%LA

The randomization scheme will be generated at Celerion by a statistician using a computerized program.

6.5 Blinding

This is an open-label study; however the site (except the pharmacy staff preparing the IPs for administration) will be blinded to the randomization sequences until they are assigned. Subjects will not be informed of the complete sequence to which they have been assigned to receive the P4M3 products.

6.6 Investigational Product Accountability and Compliance

6.6.1 Dispensing Investigational Products

From Day -2 until Day 4, P4M3 device and cartomizer will be dispensed, ready-to-use, by the Investigator or dedicated study staff, as per study design. Each dispense of the IP will be recorded in a log. The log should include subject number, date, and start and stop time of product use. The product will not be promoted for commercial distribution or test market.

Data and information contained in this document are considered to constitute trade secrets and confidential commercial information, and the legal protections provided to such trade secrets and confidential information are hereby claimed under the applicable provisions of US law. No part of this document may be publicly disclosed without the written consent of PMI.

Subjects will bring a sufficient quantity of their own e-cigarettes and e-liquids before or at the time of Admission on Day -2, which will be collected by dedicated study staff, labeled with subject number, and stored. The Investigator or dedicated study staff will dispense the subject's own e-cigarette and e-liquid as per study design. Each dispense of the IP will be recorded in a log. The log should include subject number, date, and start and stop time of product use.

6.6.2 Storage and Accountability

The P4M3 device and cartomizer will be stored in a secured storage place at the investigational site with access limited to the authorized personnel only. Full accountability of the distributed products will be ensured by designated staff. Subjects will return the P4M3 device and cartomizer immediately after use to the investigational site personnel for accountability. This will be documented in an appropriate log.

6.6.3 Investigational Product Retention

The P4M3 devices and cartomizers (dispensed and non-dispensed) will be returned to the Sponsor upon study completion.

6.6.4 Compliance to Investigational Products

Compliance will be ensured by strict distribution of the products (product by product) and collection of used P4M3 devices and cartomizers and used subjects' own e-cigarettes after each product use will be documented in appropriate logs.

6.7 Restrictions

6.7.1 Nicotine/Tobacco Product Restrictions

Subjects will not be allowed to use any nicotine/tobacco-containing products except their own closed tank/cartridge e-cigarette on Day -1 and the P4M3 test products as required per protocol from Days 1 to 4 through Discharge on Day 5 or early termination.

6.7.2 Dietary and Activity Restrictions

A standard diet will be designed by a dietician for the whole confinement period. For each meal, the caloric and fat content should be controlled in order to avoid a "high-fat" diet. A "high-fat" diet is a diet which contains "approximately 50 percent of total caloric content of the meal [from fat] and is high in calories (approximately 800 to 1000 calories) (FDA, 2002).

Subjects should refrain from ingesting foods or beverages containing grapefruit or seville-type (sour) oranges and marmalade, apple, orange, pineapple, vegetables from the mustard green family (e.g., kale, broccoli, watercress, collard greens, kohlrabi, Brussels sprouts, mustard), and charbroiled meats from 7 days prior to Day -2 and throughout the study.

Subjects are not allowed to bring their own food or beverages to the investigational site. Water, light snacks, fruits, and raw vegetables can be distributed to the subjects without restrictions at any time during confinement as long as they comply with the dietician's standard diet. Consumption of food or beverage (including water) will not be allowed during each product use on Day -1 to Day 4. The same menu and meal schedule will be administered uniformly for all subjects. Fasting state has to be observed for at least 12 hours prior to blood drawings for the safety laboratory on Day -2, Day 2, and Day 5.

Subjects should refrain from strenuous and/or unaccustomed exercise throughout the entire course of the study.

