9 STUDY ACTIVITIES

A detailed schedule of assessments can be found in [Appendix 1](#). The investigational site may adjust the start times of scheduled events as long as the necessary relative timing of the previous and subsequent events are maintained. Measurements not conducted at the exact time point, but conducted within the given time window (if applicable) do not constitute a protocol deviation but an accepted variability for the scheduled time point.

In general, if no start time for the procedure is provided, then the procedure can be performed at any time during the day.

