9.3 Baseline and Investigational Period

9.3.1 Day -1 (Baseline) to Days 1 to 4 of Investigational Product Use

On the days of fixed puffing (morning) and *ad libitum* use (afternoon) with HPT, assessments will be performed as detailed in [Table 7](#) and [Table 8](#).

Table 7. Event Schedule – Fixed Puffing and *Ad Libitum* Product Use With Subjects’ Own e-Cigarette (Days -1)

Blood sample	Procedures	Additional information
	Optional morning snack	
√	Nicotine baseline plasma sampling prior subjects’ own e-cigarette use	One blood sample will be taken prior to the start of product use (T0): 15 minutes ± 5 minutes (T-1).
	Vital signs prior product use (x1 T0)	At least 5 minutes in supine position prior to measurement
	VAS for craving prior product use (x1 T0)	
	Washout	Minimum of 10 hours
	Fixed puffing subjects’ own e-cigarette with HPT	Fixed puffing regimen comprising of 12 puffs in total at a rate of one puff every 30 seconds (± 5 seconds)
√	Plasma samples for nicotine	Post T0, blood will be drawn at the following time points: T1 after 2 minutes ± 30 seconds, T2 after 4 minutes ± 1 minute, T3 after 7 minutes ± 1 minute, T4 after 10 minutes ± 1 minute, T5 after 15 minutes ± 2 minutes, T6 after 30 minutes ± 2 minutes, T7 after 1 hour ± 5 minutes, T8 after 2 hours ± 5 minutes, T9 after 4 hours ± 5 minutes.

Data and information contained in this document are considered to constitute trade secrets and confidential commercial information, and the legal protections provided to such trade secrets and confidential information are hereby claimed under the applicable provisions of US law. No part of this document may be publicly disclosed without the written consent of PMI.

VAS Craving assessment	Post T0, VAS assessments will be assessed at the following time points 4 minutes (± 2 minutes) 10 minutes (± 2 minutes) 15 minutes (± 2 minutes) 30 minutes (± 5 minutes) 1 hour (± 10 minutes) 2 hours (± 10 minutes) 4 hours (± 10 minutes)
SQ assessment	Within 60 minutes after completion of product use
Assessment of cough (VAS, three Likert scales and one open question)	Completed by the subject on site within 30 minutes of product use
Vital signs	At least 5 minutes in supine position prior to measurement, to be conducted at 60 minutes \pm 10 minutes post end of product use
Device events malfunctions/misuse	As reported post product use
Lunch	
Vital signs pre-product use	At least 5 minutes in supine position prior to measurement
VAS for craving pre-product use (x1 T0)	

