**Table 8. Event Schedule – Fixed Puffing and *Ad Libitum* Product Use with P4M3 Variants (Days 1 to 4)**

Blood sample	Procedures	Additional information
	Optional morning snack	
	Randomization (Day 1 only)	Sequence 1: P4M3-1.7%; P4M3-1.7%LA; P4M3-3%LA; and P4M3-4%LA Sequence 2: P4M3-1.7%LA; P4M3-1.7%; P4M3-3%LA; and P4M3-4%LA
√	Nicotine baseline plasma sampling prior P4M3 variants use	One blood sample will be taken prior to the start of product use (T0): 15 minutes ± 5 minutes (T-1).
√	Clinical laboratory parameters (hematology, urine analysis, clinical chemistry) (Day 2 only)	Fasting state
	Vital signs prior product use	At least 5 minutes in supine position prior to measurement
	VAS for craving prior product use (x1 T0)	
	Washout	Minimum of 10 hours
	Fixed puffing P4M3 variants with HPT	Fixed puffing regimen comprising of 12 puffs in total at a rate of one puff every 30 seconds (± 5 seconds)
√	Plasma samples for nicotine	Post T0, blood will be drawn at the following time points: T1 after 2 minutes ± 30 seconds, T2 after 4 minutes ± 1 minute, T3 after 7 minutes ± 1 minute, T4 after 10 minutes ± 1 minute, T5 after 15 minutes ± 2 minutes, T6 after 30 minutes ± 2 minutes, T7 after 1 hour ± 5 minutes, T8 after 2 hours ± 5 minutes, T9 after 4 hours ± 5 minutes.

VAS Craving assessment	Post T0, VAS assessments will be assessed at the following time points 4 minutes (± 2 minutes) 10 minutes (± 2 minutes) 15 minutes (± 2 minutes) 30 minutes (± 5 minutes) 1 hour (± 10 minutes) 2 hours (± 10 minutes) 4 hours (± 10 minutes)
SQ assessment	Within 60 minutes after completion of product use
Assessment of cough (VAS, three Likert scales and one open question)	Completed by the subject on site within 30 minutes of product use
Vital signs	At least 5 minutes in supine position prior to measurement, to be conducted at 60 minutes ± 10 minutes post end of product use
Device events malfunctions/misuse	As reported post product use
Washout	Minimum 10 hours
Lunch	
Vital signs pre-product use	At least 5 minutes in supine position prior to measurement
VAS for craving prior product use (x1 T0)	
√ Nicotine baseline plasma sampling (x1 T0) prior P4M3 variants ad libitum use	One blood sample will be taken prior to P4M3 variants ad libitum use (T0): 15 minutes ± 5 minutes (T-1)
Ad libitum use P4M3 variants with HPT	Ad libitum use for 60 minutes (± 5 minutes) with HPT recording

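### Food before the fixed-puffing session is left open: only Day 2 of the five compared mornings has a required fast, and the morning-snack rows make no exception for the fasting draws (minor, cheap to fix)

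*Protocol*

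**What the plan says.** Section 6.7.2 of the protocol has four rules on food that bear on this point.

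- Fasting: three safety draws (Days -2, 2 and 5) carry the rule "Fasting state has to be observed for at least 12 hours prior to blood drawings for the safety laboratory". Section 7.5.1 repeats the 12 hours for every safety draw except Screening.
- Snacks: water, light snacks, fruit and raw vegetables may be given "without restrictions at any time during confinement as long as they comply with the" dietician's standard diet.
- Product use: "Consumption of food or beverage (including water) will not be allowed during each product use" on Day -1 to Day 4. The time before T0 is not covered.
- Uniformity: "The same menu and meal schedule will be administered uniformly for all subjects". This equalises subjects, not days.

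Table 7 (Day -1) and Table 8 (Days 1 to 4) both open with the row "Optional morning snack". Table 8 limits its randomization row to Day 1 and its laboratory row to Day 2, and marks the latter as fasting, but puts no day limit on the snack row. Table 9 lists the same optional snack on Day 5, where the laboratory draw is also to be made fasting.

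Section 6.3.3 fixes the order of products. Day 2 is 1.7%LA in Sequence 1 and 1.7% in Sequence 2; Day 3 is always 3%LA and Day 4 always 4%LA. The subject's own product is always used on Day -1.

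**The concern.** Section 4.2 presents fixed puffing as the regimen that shows delivery under consistent conditions, and gives the study goal as selecting the variant whose absorption is closest to that of the subject's own product. T0 is held to within 30 minutes across days. Food before T0 is not held at all: one morning has a required fast, the other four do not, and a snack is optional on all five.

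The one morning that differs is tied to product. Own product, 3%LA and 4%LA never fall on it; the two 1.7% variants do. The variant:own model in Section 12.6.2 contains sex, product and subject, so a Day 2 food effect would be read as a product effect. No analysis can later restore a food state that was never fixed.

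Separately, the unqualified snack rows in Tables 8 and 9 clash with the fasting draws on Days 2 and 5, whose panel includes fasting glucose and triglycerides (Table 2).

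**Working it through.** **Required fast by morning and product.** Inputs: Section 6.7.2 for the fasting days and Section 6.3.3 for the sequences. An 8:8 split of the 16 randomized subjects is assumed.

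| Product | Fixed-puffing day | Sessions on the required-fast morning |
|---|---|---|
| Own | Day -1 | 0 of 16 |
| 1.7% | Day 1 or 2 | 8 of 16 |
| 1.7%LA | Day 2 or 1 | 8 of 16 |
| 3%LA | Day 3 | 0 of 16 |
| 4%LA | Day 4 | 0 of 16 |

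**Shift in the variant:own ratios.** The protocol gives no figure to reproduce and no food effect, so x below is an assumption. Let a snack multiply cAUC(0-4h) or cCmax by (1 + x). Let p be snack uptake on the other mornings, equal on each, with no snack before T0 on Day 2. Half the sessions of each 1.7% variant then lack the food effect that the other mornings carry on average, and the ratio moves by the factor (1 + x)^(p/2):

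| x | p = 1 | p = 0.5 | p = 0 |
|---|---|---|---|
| 5% | 2.5% | 1.2% | 0% |
| 10% | 4.9% | 2.4% | 0% |
| 20% | 9.5% | 4.7% | 0% |

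Example: 1.10^0.5 = 1.049. If food raises exposure the ratio is too low by that factor (1/1.049 = 0.953); if food lowers it, too high. Under the same assumptions the 3%LA:own and 4%LA:own ratios do not move.

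A noise-free least-squares fit of the planned structure, with a Day 2 effect of 1.05, 1.10 or 1.20, returns factors of 1.025, 1.049 and 1.095 for the two 1.7% ratios and 1.00 for the other two. The 1.7%LA:1.7% contrast stays at 1.00, because its model has a period term.

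**Compared with the precision of the ratio.** The 90% CI factor is exp(t × s × √(2/n)), with s = √ln(1 + CV²), df = 4(n − 1), and an assumed within-subject CV of 25, 30 or 40%.

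- n = 12: 1.18, 1.22, 1.30.
- n = 16: 1.16, 1.19, 1.26.

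For the shift to equal this factor at p = 1, the food effect would have to be factor² − 1:

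- n = 12: 40, 50, 70%.
- n = 16: 34, 42, 58%.

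**The case against.** The strongest reply is that nothing in the documents says food alters inhaled nicotine, so every percentage above comes from an assumption. Even a 20% effect stays inside the confidence interval, and only secondary ratios in a study with no hypotheses are exposed. All of that stands.

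It also stands that the figures depend on uptake. The fast is tied to the laboratory draw rather than to T0, so a snack between the draw and T0 on Day 2 is not excluded and would shrink the shift. Unequal uptake on the other mornings would break the pattern, and could move the 3%LA and 4%LA ratios too.

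A further reply is that the snack row is only a drafting gap: an optional row cannot override a stated fast, and staff would probably hold the Day 2 snack until after the draw. That is likely. But doing so satisfies the laboratory rule and leaves the difference between mornings in place.

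A reader might also infer that the Day 2 fast cannot be met. With morning T0 at 0 h, ad libitum T0 lies between 10 h and 24 − 10 − 1 = 13 h. In printed order at nominal times, the evening meal follows the vital signs and starts at 12 to 15 h. A draw at T-1 on Day 2 (23.75 h) needs the last food by 11.75 h, so the meal is 0.25 to 3.25 h late. The documents do not support the stronger reading, because the printed order does not bind: under Section 9, "if no start time for the procedure is provided, then the procedure can be performed at any time during the day". Even in printed order, the favourable ends of the windows put meal start at 11.75 h and the draw at 24.33 h, a gap of 12.58 h.

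**Conclusion.** The point holds as a minor, inexpensive improvement. Food state before fixed puffing is left open and can differ by product, because the only required fast falls on a morning used solely for 1.7% and 1.7%LA. The exposed results are the secondary fixed-puffing 1.7%:own and 1.7%LA:own ratios, and the graphical dose-proportionality check of 1.7%LA against 3%LA and 4%LA.

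The size is unknown. The 2.5 to 9.5% figures are illustrative upper bounds for an assumed 5 to 20% food effect. They rest on 1:1 sequences, full and equal snack uptake on the other mornings, and no snack before T0 on Day 2.

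A reader might infer that the choice of variant or the main result is biased. The documents do not support that. The primary ad libitum endpoints come from afternoon sessions at least 10 h after morning T0, the lactic acid PK contrast has a period term, and the other mornings may be fasted as well, since the snack is optional.

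**What to change.** - Section 6.7.2 and Tables 7 and 8: on the mornings of Days -1 to 4, give no food until after fixed-puffing T0 (and, as already required, none during use). Then offer the snack at the same time after T0 each day; on Day 2, also only after the safety draw.
- Table 9: give no snack before the Day 5 fasting draw.
- Section 6.7.2: make the sentence on unrestricted snacks subject to these rules.

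This is wording only, with no added sample, visit or CRF field. The cost is that subjects wait for the morning snack until after the session. The length of the overnight interval without food may still vary between days.

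A fixed last-food clock time and a re-timed evening meal are not recommended. With a draw at T-1 and a 30-minute meal after use, ad libitum T0 would have to fall between 10 and 10.25 h (11.75 − 0.5 − 1 = 10.25). The meal would then come before the 60-minute vital signs and inside the cough, adapted mCEQ and SQ windows. That is out of proportion to the point.
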